## **8.2 Participating Study Sites, Investigators and Staff, Laboratories, and Sponsor Information**

This information is provided in the Clinical Study File.

---

CONFIDENTIAL

## 8.3 Ipilimumab and Nivolumab Dose Delays and Adjustments

No dose reductions or escalations are permitted.

### Criteria for Dose Delay

Because of the potential for clinically meaningful immuno-oncology-related AEs requiring early recognition and prompt intervention, management algorithms have been developed for the following suspected AEs: diarrhea/colitis; elevated creatinine; pneumonitis; elevated liver function tests (LFTs); elevated TSH; rash; and neurological AEs (see Section 8.3.1).

Dose delay criteria apply to all drug-related AEs (regardless of whether or not an event is attributed to nivolumab, ipilimumab, or both). All study drugs must be delayed until criteria for resumption of treatment are met.

Nivolumab and ipilimumab administration should be delayed for the following:

- Any Grade  $\geq 2$  non-skin, drug-related AE, with the following exceptions:
  - Grade 2 drug-related fatigue or laboratory abnormalities do not require a treatment delay.
- Any Grade 3 skin, drug-related AE.
- Any Grade 3 drug-related laboratory abnormality, with the following exceptions for asymptomatic amylase or lipase, AST, ALT, or total bilirubin:
  - Grade 3 amylase or lipase abnormalities that are not associated with symptoms or clinical manifestations of pancreatitis do not require a dose delay. It is recommended to consult with the Sponsor for Grade 3 amylase or lipase abnormalities.
  - If a subject has a baseline AST, ALT, or total bilirubin that is within normal limits, delay dosing for drug-related Grade  $\geq 2$  toxicity.
  - If a subject has baseline AST, ALT, or total bilirubin within the Grade 1 toxicity range, delay dosing for drug-related Grade  $\geq 3$  toxicity.
- Any AE, laboratory abnormality, or intercurrent illness that, in the judgment of the investigator, warrants delaying the dose of study medication.

### Criteria to Resume Treatment

Subjects may resume treatment with study drugs when the drug-related AE(s) resolve to Grade  $\leq 1$  or baseline value, with the following exceptions:

- Subjects may resume treatment in the presence of Grade 2 fatigue.
- Subjects who have not experienced a Grade 3 drug-related skin AE may resume treatment in the presence of Grade 2 skin toxicity.
- Subjects with baseline Grade 1 AST/ALT or total bilirubin who require dose delays for reasons other than a 2-grade shift in AST/ALT or total bilirubin may resume treatment in the presence of Grade 2 AST/ALT OR total bilirubin.
- Subjects with combined Grade 2 AST/ALT AND total bilirubin values meeting discontinuation parameters should have treatment permanently discontinued.
- Drug-related pulmonary toxicity, diarrhea, or colitis must have resolved to baseline before treatment is resumed.

---

CONFIDENTIAL

- Drug-related endocrinopathies adequately controlled with only physiologic hormone replacement may resume treatment.

If the criteria to resume treatment are met, the subject should restart treatment at the next scheduled time point per protocol. However, if the treatment is delayed past the next scheduled time point per protocol, the next scheduled time point will be delayed until dosing resumes. Doses may not be skipped. For ipilimumab, the intent is to administer all 4 doses if possible.

If treatment is delayed for > 6 weeks, the subject must be permanently discontinued from study therapy, except as specified in the discontinuation criteria.

### **Discontinuation Criteria**

Treatment should be permanently discontinued for the following:

- Any Grade 2 drug-related uveitis or eye pain or blurred vision that does not respond to topical therapy and does not improve to Grade 1 severity within the re-treatment period OR requires systemic treatment.
- Any Grade 3 non-skin, drug-related AE lasting > 7 days, with the following exceptions for drug-related laboratory abnormalities, uveitis, pneumonitis, bronchospasm, diarrhea, colitis, neurologic AE, hypersensitivity reactions, and infusion reactions:
  - Grade 3 drug-related uveitis, pneumonitis, bronchospasm, diarrhea, colitis, neurologic adverse event, hypersensitivity reaction, or infusion reaction of any duration requires discontinuation.
  - Grade 3 drug-related laboratory abnormalities do not require treatment discontinuation except those noted below:
    - Grade 3 drug-related thrombocytopenia > 7 days or associated with bleeding requires discontinuation.
    - Any drug-related LFT abnormality that meets the following criteria requires discontinuation:
      - AST or ALT > 8 x ULN.
      - Total bilirubin > 5 x ULN.
      - Concurrent AST or ALT > 3 x ULN and total bilirubin > 2 x ULN.
- Any Grade 4 drug-related AE or laboratory abnormality, except for the following events which do not require discontinuation:
  - Isolated Grade 4 amylase or lipase abnormalities that are not associated with symptoms or clinical manifestations of pancreatitis.
  - Isolated Grade 4 electrolyte imbalances/abnormalities that are not associated with clinical sequelae and are corrected with supplementation/appropriate management within 72 hours of their onset.
- Any dosing interruption lasting > 6 weeks with the following exceptions:
  - Dosing interruptions to allow for prolonged steroid tapers to manage drug-related AEs are allowed. Prior to re-initiating treatment in a subject with a dosing interruption lasting > 6 weeks, the Investigator must be consulted. Tumor assessments should continue as per protocol even if dosing is interrupted.
  - Dosing interruptions > 6 weeks that occur for non-drug-related reasons may be allowed if approved by the Investigator. Prior to re-initiating treatment in a subject with a dosing

interruption lasting > 6 weeks, the Investigator must be consulted. Tumor assessments should continue as per protocol even if dosing is interrupted.

- Any AE, laboratory abnormality, or intercurrent illness that, in the judgment of the Investigator, presents a substantial clinical risk to the subject with continued nivolumab or ipilimumab dosing.

### **Treatment of Nivolumab- or Ipilimumab-related Infusion Reactions**

Since nivolumab and ipilimumab contain only human immunoglobulin protein sequences, it is unlikely to be immunogenic and induce infusion or hypersensitivity reactions. However, if such a reaction were to occur, it might manifest with fever, chills, rigors, headache, rash, pruritus, arthralgia, hypo- or hypertension, bronchospasm, or other symptoms.

All Grade 3 or 4 infusion reactions should be reported as an SAE if criteria are met. Infusion reactions should be graded according to NCI CTCAE, Version 4.03 guidelines.

Treatment recommendations are provided below and may be modified based on local treatment standards and guidelines as appropriate:

For Grade 1 symptoms: (Mild reaction; infusion interruption not indicated; intervention not indicated)

Remain at bedside and monitor subject until recovery from symptoms. The following prophylactic premedications are recommended for future infusions: diphenhydramine 50 mg (or equivalent) and/or paracetamol (acetaminophen) 325 to 1000 mg at least 30 minutes before additional nivolumab/ipilimumab administrations.

For Grade 2 symptoms: (Moderate reaction; requires therapy or infusion interruption but responds promptly to symptomatic treatment [e.g., antihistamines, non-steroidal anti-inflammatory drugs, narcotics, corticosteroids, bronchodilators, IV fluids]; prophylactic medications indicated for 24 hours).

Stop the nivolumab or ipilimumab infusion, begin an IV infusion of normal saline, and treat the subject with diphenhydramine 50 mg IV (or equivalent) and/or paracetamol (acetaminophen) 325 to 1000 mg; remain at bedside and monitor subject until resolution of symptoms. Corticosteroid or bronchodilator therapy may also be administered as appropriate. If the infusion is interrupted, restart the infusion at 50% of the original infusion rate when symptoms resolve; if no further complications ensue after 30 minutes, the rate may be increased to 100% of the original infusion rate. Monitor subject closely. If symptoms recur then no further nivolumab or ipilimumab will be administered at that visit. Administer diphenhydramine 50 mg IV, and remain at bedside and monitor the subject until resolution of symptoms. The amount of study drug infused must be recorded on the eCRF. The following prophylactic premedications are recommended for future infusions: diphenhydramine 50 mg (or equivalent) and/or paracetamol (acetaminophen) 325 to 1000 mg should be administered at least 30 minutes before additional nivolumab or ipilimumab administrations. If necessary, corticosteroids (recommended dose: up to 25 mg of IV hydrocortisone or equivalent) may be used.

---

CONFIDENTIAL

For Grade 3 or Grade 4 symptoms: (Grade 3 [severe reaction; prolonged (i.e., not rapidly responsive to symptomatic medication and/or brief interruption of infusion); recurrence of symptoms following initial improvement; hospitalization indicated for other clinical sequelae (e.g., renal impairment, pulmonary infiltrates). Grade 4 [life-threatening reactions; pressor or ventilatory support indicated]).

Immediately discontinue infusion of nivolumab or ipilimumab. Begin an IV infusion of normal saline, and treat the subject as follows. Recommend bronchodilators, epinephrine 0.2 to 1 mg of a 1:1,000 solution for subcutaneous administration or 0.1 to 0.25 mg of a 1:10,000 solution injected slowly for IV administration, and/or diphenhydramine 50 mg IV with methylprednisolone 100 mg IV (or equivalent), as needed. Subject should be monitored until the investigator is comfortable that the symptoms will not recur. Nivolumab or ipilimumab will be permanently discontinued. Investigators should follow their institutional guidelines for the treatment of anaphylaxis. Remain at bedside and monitor subject until recovery from symptoms. In the case of late-occurring hypersensitivity symptoms (e.g., appearance of a localized or generalized pruritus within 1 week after treatment), symptomatic treatment may be given (e.g., oral antihistamine or corticosteroids).

For subjects who are expected to require more than 4 weeks of corticosteroids or other immunosuppressants to manage AEs, the following recommendations should be considered.

- Administer antimicrobial/antifungal prophylaxis per institutional guidelines to prevent opportunistic infections such as *Pneumocystis jirovecii* and fungal infections.
- Early consultation with an infectious disease specialist should be considered. Depending on the presentation, consultation with a pulmonologist for bronchoscopy or a gastroenterologist for endoscopy may also be appropriate.
- In subjects who develop recurrent AEs in the setting of ongoing or prior immunosuppressant use, an opportunistic infection should be considered in the differential diagnosis.

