### 3.1.9 Dose-limiting Toxicity

The DLT and MTD will not be defined or determined. A safety review will be conducted when 9 subjects have been accrued to Cohort A and completed the concurrent ipilimumab and nivolumab therapy. If  $\leq 7$  subjects have Grade 3 or 4 drug- or radiation-related AEs, the safety of Cohort A will be deemed acceptable and additional subjects will be accrued to Cohort B. The Cohort A assessment period for this evaluation will include the first 2 cycles of treatment, up to and including the pre-dose safety assessments scheduled for Cycle 3 (see Section 4.1.2).

Note: Grade 3 or 4 amylase or lipase abnormalities that are not associated with clinical symptoms will not be included in the Cohort A safety assessment described above.

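### Section 8.3 gives two incompatible instructions for an infusion reaction that recurs after restart: withhold drug for that visit, or discontinue permanently

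*Combined protocol and SAP*

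**What the plan says.** All the management text is in Section 8.3, under Treatment of Nivolumab- or Ipilimumab-related Infusion Reactions and under Discontinuation Criteria.

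- **Grade 2 description:** "Moderate reaction; requires therapy or infusion interruption but responds promptly to symptomatic treatment".
- **Grade 2, restart:** "If the infusion is interrupted, restart the infusion at 50% of the original infusion rate when symptoms resolve".
- **Grade 2, recurrence:** "If symptoms recur then no further nivolumab or ipilimumab will be administered at that visit".
- **Grade 2, later dosing:** "The following prophylactic premedications are recommended for future infusions: diphenhydramine 50 mg (or equivalent) and/or paracetamol (acetaminophen) 325 to 1000 mg should be administered". Nothing separates subjects who recurred from those who did not.
- **Grade 3 description:** the listed features include "recurrence of symptoms following initial improvement".
- **Grade 3 or 4 action:** "Nivolumab or ipilimumab will be permanently discontinued".
- **Discontinuation Criteria:** a Grade 3 drug-related "infusion reaction of any duration requires discontinuation".

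The infusion-reaction text also says that these reactions are graded by CTCAE v4.03, and that the treatment recommendations may be adapted to local standards. Section 7.1.3 applies CTCAE v4.03 to the severity of all adverse events.

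Grade also feeds the Cohort A rule in Section 3.1.9: if no more than 7 "subjects have Grade 3 or 4 drug- or radiation-related AEs, the safety of Cohort A will be deemed acceptable". The window is the first two cycles, up to the Cycle 3 pre-dose assessments. Only asymptomatic amylase and lipase abnormalities are left out of the count.

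**The concern.** A site that treats a reaction as Grade 2, restarts the infusion and sees symptoms return has one paragraph in front of it. That paragraph withholds drug for the day and turns to premedication for later doses. It does not say that the event may now meet the Grade 3 description, and it does not point to the Discontinuation Criteria. Another site with the same sequence of events could go straight to the Grade 3 text and stop treatment for good.

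What is at stake is first the subject: re-exposure with premedication under one reading, permanent discontinuation under the other. A secondary risk is that a site lets the paragraph it is using determine the grade it records. That grade would then enter the primary safety tables and, in Cohort A, the count that decides whether Cohort B opens.

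**Working it through.** **Do the two paragraphs describe the same event?**

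1. The Grade 2 paragraph allows a restart only after symptoms have resolved.
2. Resolution is an improvement, so any recurrence after restart follows an initial improvement.
3. That is the feature listed under Grade 3. Every recurrence on restart therefore meets the Grade 3 wording.
4. The Grade 2 paragraph limits the consequence to the current visit and then addresses later infusions. The Grade 3 text and the Discontinuation Criteria require permanent discontinuation. Both cannot be followed for the same subject.

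**Does the event have two grades?** The Grade 2 paragraph does not assign a grade to the recurrence. CTCAE v4.03 is the stated standard, and the only grade description in the protocol that names recurrence is Grade 3. The conflict is therefore in management.

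**How far could a misgrade move the Cohort A decision?**

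Inputs: the limit of 7 of 9 and the prior Grade 3/4 rate of 53%, both from Section 3.1.6. Subjects are assumed independent.

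- Plan's own figure: 7/9 = 0.778, which matches the stated 78%.
- Chance that the limit is exceeded at 53%: P(8 or more of 9) = 9 × 0.53^8 × 0.47 + 0.53^9 = 0.0263 + 0.0033 = 0.030.
- One reclassified subject moves the observed proportion by 1/9 = 11.1 percentage points. This requires a Cohort A subject who reacts within the first two cycles and has no other Grade 3/4 related event.
- To change the decision as well, exactly 7 of the other 8 subjects must be affected: 8 × 0.53^7 × 0.47 = 0.044.

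The documents give no frequency for such subjects, so their share r is assumed and added to 53%:

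| Assumed r | P(limit exceeded), recurrence recorded as Grade 3 | P(limit exceeded), recurrence left at Grade 2 |
|---|---|---|
| 1% | 0.034 | 0.030 |
| 2% | 0.039 | 0.030 |
| 5% | 0.056 | 0.030 |
| 10% | 0.098 | 0.030 |

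Section 3.1.6 does not say over what period the 53% was observed, and it states that no historical rate exists for the triple combination. The 0.044 depends on that rate. The same formula gives 8 × 0.43^7 × 0.57 = 0.012 at 43%, 8 × 0.63^7 × 0.37 = 0.117 at 63%, and 8 × 0.70^7 × 0.30 = 0.198 at 70%. Each of these is conditional on such a subject existing at all.

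**The case against.** The strongest reply is that the text can be read in sequence. Withholding drug for the rest of the visit is an immediate bedside step. It does not authorise redosing, and it is compatible with a later decision to discontinue. The premedication sentence closes the whole Grade 2 paragraph and serves mainly subjects who did not recur. Once the event is graded, the Discontinuation Criteria supply a consequence. Unlike the treatment paragraphs, those criteria are not described as locally modifiable. Section 3.1.8 sends discontinuations to Section 8.3, and Section 3.1.10 lists the Section 8.3 criteria as a reason for withdrawal from treatment.

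Much of this stands, and it rules out three stronger readings that a reader might infer:

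- **That the protocol gives one event two grades.** It does not; grading is fixed to CTCAE v4.03, and a Grade 2 record would come from a site departing from that.
- **That nothing in the protocol bears on which instruction governs.** The sections just cited do bear on it, though none mentions recurrence on restart.
- **That the opening of Cohort B hangs on this wording.** That needs several conditions to hold together, and the protocol itself regards such reactions as unlikely.

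What the reply does not remove is the gap in the Grade 2 paragraph. It deals with recurrence explicitly, confines the consequence to the visit, makes no exception when it turns to later infusions, and refers to no other rule. The sequential reading has to be supplied by the reader, and local adaptation of the recommendations at three sites leaves room for different handling.

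**Conclusion.** The management conflict is real and can be seen in the current text without any outside source. Its importance lies in contradictory instructions on re-exposure after a recurrent reaction.

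The statistical consequence is conditional and likely very small. It requires a site to grade by the paragraph it is following. For the Cohort A count it also requires a first-two-cycle event in a subject with no other Grade 3/4 related event. At 53%, an assumed 1% to 2% of such subjects raises the chance of exceeding the limit from 0.030 to between 0.034 and 0.039. These figures rest on independence between subjects, on the 53% applying within the window, and on the assumed share.

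Severity: minor. Which clinical instruction is right is not a matter for this review.

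**What to change.** Reconcile the Grade 2 paragraph, the Grade 3/4 text and the Discontinuation Criteria in Section 8.3 so that recurrence on restart has one stated consequence, consistent with its CTCAE v4.03 grade. Add a cross-reference from the Grade 2 paragraph to the rule that governs. The clinical team decides which rule that is.

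Sections 3.1.9 and 4.1.2 need no addition. Section 4.1.2, Section 7.1.3 and the infusion-reaction text already tie these events to CTCAE v4.03, and the Cohort A rule already counts all related Grade 3/4 events apart from the amylase and lipase exception.

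The cost is one or two sentences in the next amendment, with no new data, visits or procedures.

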### **8.3.1 Management Algorithms for Adverse Events Associated with Immuno-oncology Agents**

Please refer to the most current version of the nivolumab IB for current recommendations for management of a specific Adverse Event of interest. The following management algorithms are available in the Appendix of the IB:

- GI AE Management
- Renal AE Management
- Pulmonary AE Management
- Hepatic AE Management
- Endocrinopathy Management
- Skin AE Management
- Neurological AE Management

---

CONFIDENTIAL

## 8.4 RECIST 1.1 and irRECIST Guidelines

The Response Evaluation Criteria in Solid Tumors (RECIST) guidelines were revised in 2009 as RECIST 1.1.(47) These guidelines have been the widely accepted criteria to assess response and progression in solid tumors; however, limitations have been noted in the use of RECIST 1.1 for immunotherapy trials. With immunotherapeutic agents, clinical trials have shown that complete response, partial response, or stable disease status can still be achieved after an initial increase in overall tumor burden, and regression of initial lesions may occur despite development of new lesions. The Immune-related Response Criteria (irRC) were developed to address the need for response criteria in an immunotherapy setting.(13) The main difference with irRC was that it considered the subject's total tumor burden at each subsequent assessment and required confirmation of suspected disease progression with subsequent imaging, approximately four weeks later. In addition, a greater number of lesions (10 vs. 5) were measured in a bidimensional manner instead of unidimensionally as in RECIST 1.1. In 2013, Nishino et al. demonstrated that immune-related response criteria using unidimensional measurements were highly concordant with the bidimensional results of irRC, but with less measurement variability.(48) Based on these findings and in order to utilize both the established criteria of irRC and RECIST 1.1, the two systems have been adapted, modified, and combined into the Immune-related Response Evaluation Criteria in Solid Tumors (irRECIST).(49) The adapted irRECIST criteria are modifications to the irRC, incorporating the findings of Nishino et al. and the advantages of RECIST 1.1 while overcoming the shortcomings of each of the other guidelines. The guidelines for RECIST 1.1 are summarized below, followed by a summary for irRECIST.

### RECIST 1.1

The following section outlines the RECIST 1.1 guidelines as published (47) and as summarized by National Cancer Institute for CTEP-involved clinical trials.

#### I. Disease Parameters for RECIST 1.1

Changes in the largest diameter (unidimensional measurement) of the tumor lesions and the shortest diameter in the case of malignant lymph nodes are used in the RECIST 1.1 criteria.

Measurable disease. Measurable lesions are defined as those that can be accurately measured in at least one dimension (longest diameter to be recorded) as  $\geq 20$  mm by chest x-ray, as  $\geq 10$  mm with CT scan, or  $\geq 10$  mm with calipers by clinical exam. All tumor measurements must be recorded in millimeters (or decimal fractions of centimeters).

Note: Tumor lesions that are situated in a previously irradiated area might or might not be considered measurable. *If the investigator thinks it appropriate to include them, the conditions under which such lesions should be considered must be defined in the protocol.*

**NOTE for irRECIST: During target lesion selection the radiologist will consider information on the anatomical sites of previous intervention (e.g. previous irradiation, RF-ablation, TACE, surgery, etc.). Lesions undergoing prior intervention will not be selected as target lesions unless there has been a demonstration of progress in the lesion.**

CONFIDENTIAL

Malignant lymph nodes. To be considered pathologically enlarged and measurable, a lymph node must be  $\geq 15$  mm in short axis when assessed by CT scan (CT scan slice thickness recommended to be no greater than 5 mm). At baseline and in follow-up, only the short axis will be measured and followed.

Non-measurable disease. All other lesions (or sites of disease), including small lesions (longest diameter  $< 10$  mm or pathological lymph nodes with  $\geq 10$  to  $< 15$  mm short axis), are considered non-measurable disease. Bone lesions, leptomeningeal disease, ascites, pleural/pericardial effusions, lymphangitis cutis/pulmonitis, inflammatory breast disease, and abdominal masses (not followed by CT or MRI), are considered as non-measurable.

Note: Cystic lesions that meet the criteria for radiographically defined simple cysts should not be considered as malignant lesions (neither measurable nor non-measurable) since they are, by definition, simple cysts. 'Cystic lesions' thought to represent cystic metastases can be considered as measurable lesions, if they meet the definition of measurability described above. However, if non-cystic lesions are present in the same patient, these are preferred for selection as target lesions.

